ID: 69227
NCT05698368
March 2023

Digital Knee Osteoarthritis Mindset Intervention

Supplement 1.

Protocol: A Digital Mindset Intervention to Improve Pain and Exercise Participation in Individuals With Knee Osteoarthritis: A Randomized Clinical Trial

SPIRIT Checklist

Investigators

[name]
[name]
[name]
[name]
[name]
[name]
[name]
[name]
[name]
[name]

Background and Significance

Osteoarthritis affects 7% of the global population and is a leading cause of disability globally. Physical activity improves health outcomes, weight management, and knee function for people with knee osteoarthritis and should be considered first-line treatment. Yet, physical activity levels in this population are low compared to those without knee osteoarthritis.

Emerging research has highlighted the powerful influence of mindsets about exercise on engagement in physical activity. Mindsets are core assumptions about a domain or category that orient individuals to a particular set of attributions, expectations, and goals (a "meaning system"). In individuals with knee osteoarthritis, mindsets about the appeal of physical activity relate to future physical activity levels and one's chosen symptom management strategy, and mindsets about osteoarthritis relate to knee symptoms.

We developed a digital mindset intervention to improve mindsets about exercise and osteoarthritis in individuals with knee osteoarthritis. We piloted the intervention on 21 individuals with knee osteoarthritis throughout the United States. Participants improved in exercise and osteoarthritis mindsets. However, this was a small sample size, a control group was not used, and it was cross-sectional; thus, not able to evaluate changes in physical activity and osteoarthritis symptoms. A large randomized trial is therefore needed to evaluate if our mindset intervention leads to improvements in

physical activity levels and osteoarthritis symptoms and, further, if these changes are due to more adaptive mindsets about exercise and osteoarthritis.

Supplement 1 Table 1. Study Meta-data

Data category	Information
Primary registry and trial identifying number	ClinicalTrials.gov: NCT05698368
Date of registration in primary registry	January 2023
Secondary identifying numbers	IRB-69227
Source(s) of monetary or material support	
The Wu Tsai Human Performance Alliance at Stanford University and the Joe and Clara Tsai Foundation. The Stanford Catalyst for Collaborative Solutions; the Mobilize Center, which is supported by the National Institute of Biomedical Imaging and Bioengineering (NIBIB) and the Eunice Kennedy Shriver National Institute Of Child Health & Human Development (NICHD) of the National Institutes of Health (NIH) under Grant P41EB027060; and the Center for Reliable Sensor Technology-Based Outcomes for Rehabilitation (RESTORE), which is supported by the Eunice Kennedy Shriver National Institute Of Child Health & Human Development (NICHD) and the National Institute Of Neurological Disorders And Stroke (NINDS) of the National Institutes of Health (NIH) under Grant No. P2CHD101913.

Primary sponsor	Stanford University
Contact for public queries	[name] Stanford University [contact]
Contact for scientific queries	[name] Stanford University [contact]
Title	A Digital Mindset Intervention to Improve Pain and Exercise Participation in Individuals With Knee Osteoarthritis: A Randomized, Parallel-group Study
Countries of recruitment	USA
Health condition(s) or problem(s) studied	Knee osteoarthritis
Study type	Interventional Allocation: randomized Intervention model: parallel assignment Masking: Subjects not blind; outcomes assessor blind Primary purpose: Supportive Care
Date of first enrolment	April 2023
Target sample size	501

Choice of comparator

Education and exercise are recommended as first-line treatment for osteoarthritis, but often, “treatment as usual” is pain medication and, eventually, surgery. If patients want information about osteoarthritis, sometimes they are given a pamphlet about osteoarthritis by their doctor. Otherwise, they are left to research osteoarthritis on their own. Our comparator is education videos about osteoarthritis that one would typically find on the internet. While accurate, this information does not typically (or intentionally) target mindset and, as shown in the low physical activity levels and adherence to exercise, does not successfully support behavior change. As this does not put

participants at risk, we expect that it will neither improve nor worsen their physical or psychological states.

Supplement 1 Table 2. Study Objectives

Primary Objectives	
Primary outcomes	
Primary outcomes assessed at T2 (change from baseline):
 
(i) Exercise mindset using the Mindset about the Process of Health – Exercise scale. This one-factor scale was developed and validated¹ to assess mindset about the process of engaging in physical activity (e.g., physical activity is difficult/easy, unpleasant/pleasurable, boring/fun). The scale consists of 7 items and is measured on a 4-point scale and scored from 1 to 4, with a higher score reflecting a more appeal-focused mindset about exercise
 
(ii) Osteoarthritis mindsets using the Illness Mindset Inventory. The Illness Mindset Inventory measures three mindsets about the nature and meaning of illness: that it is a catastrophe, manageable, or an opportunity. The scale consists of 20 items measured on a 6-point scale and scored from 1 to 6, with 10 of those questions capturing mindsets about chronic illness. The extent to which a participant endorsed each mindset was obtained by calculating the respective mean scores. A higher score indicates greater agreement with the mindset. This Illness Mindset Inventory is valid and reliable in individuals with knee osteoarthritis². We adapted the scale to focus on mindsets about "knee osteoarthritis" as opposed to "chronic disease."
 
Primary outcomes assessed at T3 (change from baseline):
 
(i) Knee pain using the question, "What was your average osteoarthritis-related pain over the past week?" and measured on an 11-point Numeric Rating Scale (NRS) from 0 (no pain at all) to 10 (the worst pain imaginable)
 
(ii) Physical activity using the Physical Activity Scale for the Elderly (PASE). The PASE asks respondents about the frequency of light, moderate, and strenuous work and leisure activities and is a validated measure of self-reported physical activity for individuals with osteoarthritis³. The scale is scored from 0 to 793 with higher scores indicating higher levels of physical activity.

Secondary Objectives	
Key secondary	Secondary outcomes assessed at T2 (change from baseline):


outcomes
	
(i) Knee osteoarthritis knowledge by the Knee Osteoarthritis Knowledge Scale⁴. The Knee Osteoarthritis Knowledge Scale is scored from 11-55 and measures knowledge about osteoarthritis in individuals with knee or hip osteoarthritis
 
(ii) Body mindsets using the Illness Mindset Inventory. In addition to mindsets about chronic illness, the Illness Mindset Inventory measures three mindsets about the nature of the body in the context of a chronic illness: that it is adversarial, responsive, or resilient
 
(iii) Activity adequacy mindsets using the Adequacy of Activity Mindset Measure⁵. This scale was developed to assess mindsets about the adequacy and benefits of one's physical activity as it relates to health. The scale consists of 5 items measured on a 7-point scale and scored from 1 to 7, with a higher score reflecting a more adaptive mindset about the benefits and risks associated with current levels of physical activity.
 
Secondary outcomes assessed at T3 (change from baseline):
 
(i) Knee pain and functioning using the Short version of the Western Ontario and McMaster Universities Arthritis Index (shortMAC). The shortMAC is a disease-specific 12-item measure of knee symptoms and has shown to be valid and reliable in patients with knee osteoarthritis⁶. We evaluated the measure divided into two subscales: pain and function
 
(ii) Perceived need for surgery using the single question, "How likely do you think you are of needing knee replacement surgery in the future?" It was answered on the Likert scale from 1 (very unlikely) to 5 (very likely)
 
(iii) Chosen symptom management strategies using the single question, "Which of the following are ways in which you manage and/or improve your osteoarthritis symptoms? Please select all that apply." It was answered via multiple choice with a multiple-selection option. The options available were the most commonly identified responses as determined by a previous study⁷
 
(iv) Fear of movement using the Brief Fear of Movement Scale for Osteoarthritis⁸. The Brief Fear of Movement Scale for Osteoarthritis is a 6-item scale validated to assess fear of movement in individuals with osteoarthritis
 
(v) Arthritis self-efficacy using the Arthritis-Self Efficacy Scale. This scale is scored from 1 to 10, with higher scores indicating greater self-efficacy, and was divided into the "pain" and "other symptoms" subscales
 
(vi) Physical and Mental Health using the PROMIS v.1.1 Global Health Short Form⁹. This scale is a 10-item survey that measures overall physical function, fatigue, pain, emotional distress, and

-----------------	--

	
social health in healthy and clinical adult populations¹⁰. We evaluated the measure divided into its two subscales: physical health and mental health¹¹.

--	---

Key secondary outcomes
	
Secondary outcomes assessed at T2 (change from baseline):
 
 (i) Knee osteoarthritis knowledge by the Knee Osteoarthritis Knowledge Scale⁴. The Knee Osteoarthritis Knowledge Scale is scored from 11-55 and measures knowledge about osteoarthritis in individuals with knee or hip osteoarthritis (ii) Body mindsets using the Illness Mindset Inventory. In addition to mindsets about chronic illness, the Illness Mindset Inventory measures three mindsets about the nature of the body in the context of a chronic illness: that it is adversarial, responsive, or resilient (iii) Activity adequacy mindsets using the Adequacy of Activity Mindset Measure⁵. This scale was developed to assess mindsets about the adequacy and benefits of one's physical activity as it relates to health. The scale consists of 5 items measured on a 7-point scale and scored from 1 to 7, with a higher score reflecting a more adaptive mindset about the benefits and risks associated with current levels of physical activity. 
Secondary outcomes assessed at T3 (change from baseline):
 
 (i) Knee pain and functioning using the Short version of the Western Ontario and McMaster Universities Arthritis Index (shortMAC). The shortMAC is a disease-specific 12-item measure of knee symptoms and has shown to be valid and reliable in patients with knee osteoarthritis⁶. We evaluated the measure divided into two subscales: pain and function (ii) Perceived need for surgery using the single question, "How likely do you think you are of needing knee replacement surgery in the future?" It was answered on the Likert scale from 1 (very unlikely) to 5 (very likely) (iii) Chosen symptom management strategies using the single question, "Which of the following are ways in which you manage and/or improve your osteoarthritis symptoms? Please select all that apply." It was answered via multiple choice with a multiple-selection option. The options available were the most commonly identified responses as determined by a previous study⁷ (iv) Fear of movement using the Brief Fear of Movement Scale for Osteoarthritis⁸. The Brief Fear of Movement Scale for
-------------------------------	--

	
Osteoarthritis is a 6-item scale validated to assess fear of movement in individuals with osteoarthritis
 
(v) Arthritis self-efficacy using the Arthritis-Self Efficacy Scale. This scale is scored from 1 to 10, with higher scores indicating greater self-efficacy, and was divided into the "pain" and "other symptoms" subscales
 
(vi) Physical and Mental Health using the PROMIS v.1.1 Global Health Short Form⁹. This scale is a 10-item survey that measures overall physical function, fatigue, pain, emotional distress, and social health in healthy and clinical adult populations¹⁰. We evaluated the measure divided into its two subscales: physical health and mental health¹¹.

--	--

Research Hypotheses

Hypothesis 1. A digital education and mindset intervention will significantly improve mindsets about the process of exercising and osteoarthritis among adults aged ≥ 45 years with knee osteoarthritis compared to an active comparison education intervention and no-intervention immediately post-intervention.

Hypothesis 2. A digital education and mindset intervention will significantly reduce knee pain and increase physical activity levels among adults aged ≥ 45 years with knee osteoarthritis compared to an active comparison education intervention and a no-intervention control group one-month post-intervention.

Hypothesis 3. A digital education and mindset intervention will significantly improve knee osteoarthritis knowledge and mindsets about activity adequacy and the body among adults aged ≥ 45 years with knee osteoarthritis compared to an active comparison education intervention and a no intervention control group immediately post-intervention.

Hypothesis 4. A digital education and mindset intervention will significantly improve knee pain and function, perceived need for surgery, symptom management, arthritis self-efficacy, fear of movement, physical health, mental health, among adults aged ≥ 45 years with knee osteoarthritis compared to an active-comparator education group and a no-intervention control group one-month post-intervention.

Key Personnel

Trial Coordinator

[name], [contact]
 Department of Bioengineering
 Stanford University, Stanford, California, USA

Statisticians

[name]
Department of Statistics
Stanford University, Stanford, California, USA

[name]
Department of Statistics
Stanford University, Stanford, California, USA

Trial Design

We will randomize 505 individuals aged ≥ 45 years with knee osteoarthritis into one of three groups with 1:1:1 group allocation: the Mindset Group (participants receive a digital mindset intervention to improve mindsets about osteoarthritis and exercise), the Education Group (Participants receive a series of osteoarthritis education videos and reflective questions that matches the digital mindset intervention in duration and attention), or the No-Intervention Group (participants take the same surveys as the other groups at the same time points, but do not receive any additional content). Participants will complete an initial baseline survey and be randomized one week later. Those randomized to the Mindset and Education Groups will have one week to complete the self-paced online programs. All groups complete osteoarthritis knowledge and mindset surveys at this timepoint. One-month later, participants will receive a follow-up questionnaire.

Study Setting

The study will be conducted entirely online.

Eligibility Criteria

Inclusion Criteria:

- Over 45 years of age
- Self-reported doctor's diagnosis of knee osteoarthritis OR meets the National Institute for Health and Care Excellence osteoarthritis clinical criteria (activity-related knee pain and no knee morning stiffness lasting ≥ 30 minutes)
- Knee pain for at least 3 months
- Ability to walk unaided
- Can read and write in English
- Consistent internet access
- Willingness and ability to comply with the study requirements

Exclusion criteria:

- Past total knee arthroplasty or scheduled surgical procedure on any back or

- lower limb with osteoarthritis within the next 12 months
- Recent serious injury (within the past 2 months) on the knee(s) with osteoarthritis
- Any condition making it unsafe to participate in physical activity
- Intra-articular therapy within the past 6 months (e.g. injections such as corticosteroids and hyaluronic acid)
- Participates in physical exercise for 30 minutes or more 5 days per week

Interventions

Intervention(s)	
Mindset Group: Participants receive a digital mindset intervention to improve mindsets about osteoarthritis and exercise.
 
Education Group (active comparison): Participants receive a series of osteoarthritis education videos and reflective questions that matches the digital mindset intervention in duration and attention.
 
No-Intervention (control): Participants take the same surveys as the other groups at the same time points, but do not receive any additional content.

-----------------	--

Modifications

Discontinuation of the program due to psychological disturbance. We do not expect participants to have a psychological disturbance due to the mindset intervention or active comparator program. In the case that someone refuses to continue the study due to a psychological disturbance from participation, this should be reported as an adverse event.

Adherence

[figure not shown]
Adherence reminders will be in the form of emails. Three reminders will be sent out: once before the deadline, on the deadline, and the day after the deadline. Reminders will include the importance of completing the section in order to remain in the study. Reminders will also include a flow chart of the study timeline and components, with the relevant section highlighted. Participants will be able reply to the study coordinator with questions.

Concomitant Care

Participation is at the discretion of the participants. Thus, the other option for participants is to not participate in the study.

Prohibited Concomitant Treatment. Additional physical therapy treatment is not permitted during the study as it would interfere with the main outcomes of our study.

Study Flow and Timeline

Supplement 1 Figure 1. Study flow and timeline.

Sample Size

The efficacy of the mindset intervention will be deemed successful if enhancements in either or both key outcomes, namely pain intensity (NRS) or physical activity levels (PASE), are observed. Anticipating modest effect sizes between the mindset and educational cohorts, we conducted a preliminary power analysis, similar to prior online education studies for knee osteoarthritis^{12,13}, using G*Power 3.1 with a presumed effect size of 0.3 (see below). This analysis involved comparing the mindset group against both the education and no-intervention groups, leading to four distinct comparisons. These assessments are planned to be executed at a 5% significance level, aiming for an 80% probability of discerning a noticeable improvement in delta. Based on Boswell et al.⁷, we estimated the standard deviations for PASE and pain at 70.28 and 1.67, respectively. A 26-point difference in PASE was selected as the target delta. While no clinically significant benchmarks for PASE has been established, the intervention's focus on promoting walking and moderate exercise led us to define this delta as the equivalent shift in walking and light exercise frequency from “seldom” (<1 hour per day) to “sometimes” (1-2 hours per day), as per the PASE scale, giving a goal of 26 points. This determination necessitates a sample size of 139 participants per group, totaling 417. To compensate for an anticipated 20% dropout rate, we plan to enroll 501 participants. This sample size is adequately powered to detect a clinically relevant difference of 2 points in NRS pain¹⁴.

A priori power analysis

[name]

11/29/2022

Let, y_i^b represents outcome at baseline and y_i^f represents outcome at follow-up for i^{th} person in treatment group, and \bar{y}^b and \bar{y}^f represents respective means. Similarly, x_i^b represents outcome at baseline and x_i^f represents outcome at follow-up for i^{th} person in control group, and \bar{x}^b and \bar{x}^f represents respective means.

Assumption: Let $x_i^f - x_i^b \sim \mathcal{N}(\Delta_1, \sigma^2)$ and $y_i^f - y_i^b \sim \mathcal{N}(\Delta_2, \sigma^2)$.

Let's say $\Delta = \Delta_2 - \Delta_1$, we want to test the hypothesis

$$H_0 : \Delta = 0$$

$$\text{v/s } H_1 : \Delta > 0$$

Under H_0 , $T = (\bar{y}^f - \bar{y}^b) - (\bar{x}^f - \bar{x}^b) \sim \mathcal{N}(0, 2\sigma^2/n)$. We reject H_0 if $\frac{T}{\sqrt{2\sigma^2/n}} > z_{1-\alpha}$. We want n so that power at Δ is $1 - \beta$, i.e.,

[figure not shown]
$$P_{\Delta} \left(\frac{T}{\sqrt{2\sigma^2/n}} > z_{1-\alpha} \right) \geq 1 - \beta$$

which is equivalent to

$$n \geq \frac{2\sigma^2(z_{1-\alpha} + z_{1-\beta})^2}{\Delta^2}$$

[figure not shown]
For our analysis, we choose $\alpha = 0.05$, and try four different values of β , 0.05, 0.10, 0.15, and 0.20. We estimate σ from pilot data.

Outcome variable, PASE

[figure not shown]
[figure not shown]

sigma = 70.27939

A priori sample size analysis for outcome variable, PASE

[figure not shown]

Pain Scores

sigma = 1.670426

A priori sample size analysis for outcome variable, pain

Recruitment

Participants will be recruited through paid online and social media advertising and local flyer postings.

Allocation

We will use the randomizer function in Qualtrics to randomize participants into one of three groups (1:1:1): the Mindset Group, the Education Group (active comparison), or the No-Intervention Group (control).

Blinding (Masking)

During the informed consent process, participants will be informed that the purpose of the study is to understand the effect of a new online osteoarthritis program and that they will be randomized to either a no-intervention group or one of two different sets of videos and reflective questions. Participants will be aware of whether they are randomized to an online program; however, the differences in content between the two programs and the hypotheses of the study will not be revealed. The biostatistician performing the data analysis will be blinded to the group labels.

Data Collection, Management, and Access

All data will be collected through the Qualtrics online survey software. Qualtrics encrypts all transmitted data using Transport Layer Security and hosts data on data centers that are independently audited using the industry standard SSAE-18 method. Stanford University has a Qualtrics license for research use, and data obtained from the Qualtrics platform can only be accessed through a secure login. Data will be exported to Microsoft Excel and securely stored for use by the research team. Only after de-identification may the data be shared outside of the research team.

Missing Data

Participants who did not complete a survey entirely were removed from the study and not sent the follow-up survey. Each question of each survey was “force response,” meaning that if a participant completed the survey, no answers would be missing from the response. Thus, no methods for missing data were implemented.

Statistical Methods

Statistical analysis will be carried out in R¹⁵ by a blinded statistician, [name], with no knowledge of group allocation.

Standard descriptive statistics will be presented for all participant characteristic measures at baseline. Prior to analysis, t-tests for continuous variables and chi-square (χ^2) tests for categorical variables will be conducted to test the equality of means of baseline characteristics. Additionally, baseline characteristic comparisons between participants who completed the study and those who dropped out will be reported.

Changes in primary and secondary mindsets post-intervention will be compared among the mindset intervention group versus the active attention control (education group) and the no-intervention control group. We will present standard descriptive statistics of and calculate changes from baseline to post-intervention for the mindsets and knee osteoarthritis knowledge and from baseline to one-month follow-up for all other outcome variables. Changes will be presented as the mean change with 95% confidence intervals, along with Cohen d, using the following formula:

$$cohen\ d = \frac{\bar{x}_2 - \bar{x}_1}{s}$$

where \bar{x}_2 denotes the mean of variable after intervention, \bar{x}_1 denotes the mean of variable before intervention, and s denotes the standard deviation of the change in the variable due to intervention.

We will perform the t-test to compare the change in outcome variables post-intervention and at follow-up between the mindset group and the education and no-intervention groups. We assume the equality of variance for the changes. The t-statistic is given by:

$$\frac{\bar{X} - \bar{Y}}{s_{pooled} \sqrt{\frac{1}{m} + \frac{1}{n}}}$$

where \bar{X} is the mean of changes in the first group and \bar{Y} is the mean of the changes in the second group, s_{pooled} is the pooled standard deviation from the two groups. We assume that there were m people in the first group and n people in the second group. After calculating the t-statistics, the p-values will be computed to estimate the statistical significance of differences in changes between groups. We will perform Bonferonni correction for the four comparisons (e.g., the mindset group vs. the education group and the mindset group vs. the no-intervention group for pain and physical activity at one-month follow-up), which adjusts the significance threshold to $P = 0.0125$. The comparison of the education group to the no-intervention group will not be a primary comparison.

Data Monitoring

The trial coordinator will provide ongoing project oversight and will meet regularly with the senior investigators throughout the project period to provide study feedback including recruitment, retention, and adverse events. During the study, participants have access to email the study coordinator at any time to report adverse events.

Harms

The potential harms associated with this study include psychological complications resulting from the assessments or mindset and education programs or medical risks due to increasing physical activity levels. There is a small risk that individuals completing psychological questionnaires may become distressed, but there is no evidence of resulting psychological dysfunction. We performed pilot testing of the program and questionnaires in which there was no evidence of psychological complications or the risk of such complications. Further, while the program presents the benefits of physical activity, no specific programs are requested for participation and participants are encouraged to go slow and listen to their bodies.

Therefore, no harm or adverse events are foreseen in this study. However, if a complaint or adverse event arises, the research team will discuss and take appropriate action to manage the issue. Any serious adverse event or harm reported by participants will be recorded and reported.

Research Ethics Approval

The study protocol, consent form, and recruitment material will be approved by the Stanford University Research Compliance Office Institutional Review Board.

Protocol Amendments

Protocol amendments will be documented and reported.

Consent Or Assent

Participants will be directed from recruitment materials to a RedCap survey. The survey will first be provided with information on the purpose of the study and the requirements for participation. After that, participants will be given a survey to determine whether they can participate. If participants pass the qualifying survey, they will be directed to the online consent form, where they have the option to consent to participate in the study digitally.

Confidentiality

Personal or identifiable information obtained during this study is considered confidential. Participant confidentiality will be ensured by using identification code numbers corresponding to data across time points. Identifiable data will not be included in the dissemination of the manuscript and its accompanying data. See Data Management for additional information on the security of personal data.

Declaration Of Interests

None of the investigator team has any financial or other competing interests to declare.

Ancillary And Post-Trial Care

Participants who agree to be contacted for future research during the consent process may be contacted for ancillary studies. Any ancillary studies will be submitted to the Institutional Review Board for approval.

After study completion, all participants will be offered the mindset intervention program.

Dissemination Policy

The study will be submitted to peer-reviewed journals for publication. The results will be presented at national and international conferences. The results may also be shared in news outlets, such as online articles, newspapers, and magazines. Participant identity will not be disclosed when publishing or presenting the results. Participants will be informed of the results if requested.

References

2. Zion S. *From Cancer to COVID-19: The Self-Fulfilling Effects of Illness Mindsets on Physical, Social, and Emotional Functioning*. Stanford University; 2021.

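### The masking entry claims a blind outcome assessor, but every outcome is self-reported by participants who know whether they received a program; the only blinded person described is the statistician.

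*Combined protocol and SAP*

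**What the plan says.** Supplement 1 Table 1, under Study type, describes the masking as "Masking: Subjects not blind; outcomes assessor blind".

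The rest of the protocol describes who supplies the outcome data:

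- **Setting and collection.** Study Setting: "The study will be conducted entirely online". Data Collection, Management, and Access: "All data will be collected through the Qualtrics online survey software".
- **Outcomes.** In Supplement 1 Table 2, pain at T3 is one question put to the participant ("What was your average osteoarthritis-related pain over the past week"), rated 0 to 10. Physical activity is the PASE, which "is a validated measure of self-reported physical activity for individuals with osteoarthritis". The mindset outcomes at T2 and all the secondary outcomes are likewise scales or single questions that the participant answers.
- **What participants know.** Blinding (Masking): "Participants will be aware of whether they are randomized to an online program". Between the two programs, "the differences in content between the two programs and the hypotheses of the study will not be revealed".
- **Who is blinded.** The same section says: "The biostatistician performing the data analysis will be blinded to the group labels". Statistical Methods repeats that the statistician is blinded. No other blinded role appears.

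Statistical Methods defines four Bonferroni-corrected comparisons at P = 0.0125: Mindset against Education and against No-Intervention, each for pain and physical activity at one month.

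**The concern.** When outcomes are self-reported, the participant is the assessor. An entry that calls subjects not blind and the assessor blind then says two incompatible things about the same person. Blinding the analyst protects the analysis from selective choices. It does nothing to the ratings themselves.

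This matters most against No-Intervention. Those participants know they received no program, while Mindset participants know they received one, and both then rate their own pain and activity. A difference in expectation or in willingness to report improvement feeds directly into those comparisons. A reader who relies on the metadata table would credit them with a protection they lack.

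**Working it through.** **Step 1. Set the entry against the protocol.**

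| Question | What the protocol describes |
|---|---|
| Rater, interviewer, examiner or device supplying outcome data | None |
| Outcomes that are not self-reported | None among the primary or secondary outcomes |
| Do participants know program versus no program? | Yes |
| Do program participants know how the two programs differ, or the hypotheses? | These are withheld |
| Who is blinded to group labels? | The statistician |

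Masking of the assessor by contrast:

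| Contrast | Assessor | Masking |
|---|---|---|
| Mindset vs No-Intervention: pain and PASE at T3 (2 of the 4 corrected comparisons) | Participant | None as to program versus no program |
| Mindset vs No-Intervention: exercise and osteoarthritis mindsets at T2 (also called primary) | Participant | None as to program versus no program |
| Mindset vs Education: all outcomes | Participant | Partial: content differences and hypotheses withheld |

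**Step 2. Reproduce the plan's sample size.** The inputs from the Sample Size section are a PASE difference of 26, an SD of 70.28 and 80% power. From Statistical Methods, the threshold is 0.05/4 = 0.0125. The power analysis uses a one-sided formula:

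n = 2 × SD² × (z₁₋α + z₁₋β)² / Δ² = 2 × 70.28² × (2.241 + 0.842)² / 26² = 138.9, so 139 per group.

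This matches the stated 139 (417 in total). Correcting the masking entry does not change it.

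**Step 3. Illustrate how much a reporting difference could matter.** The documents give no size for reporting bias, so the shifts below are assumptions. The other assumptions are no true effect, 139 per group, the plan's SDs (1.67 for pain, 70.28 for PASE) taken as SDs of change, and a two-sided test at 0.0125 (critical z = 2.498).

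Standard error in SD units: √(2/139) = 0.120. In raw units this is 1.67 × 0.120 = 0.200 NRS points and 70.28 × 0.120 = 8.43 PASE points.

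With a differential shift of b SDs in favour of Mindset, the chance of a significant result is close to 1 − Φ(2.498 − b/0.120):

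| b (SD) | NRS points | PASE points | b/0.120 | Chance of significance |
|---|---|---|---|---|
| 0 | 0 | 0 | 0 | 1.25% (both tails) |
| 0.1 | 0.17 | 7.0 | 0.834 | about 5% |
| 0.2 | 0.33 | 14.1 | 1.667 | about 20% |
| 0.3 | 0.50 | 21.1 | 2.501 | about 50% |

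Statistical Methods does not say whether the tests are one- or two-sided. With the one-sided critical value of the power analysis (2.241), the same formula gives 1 − Φ(2.241 − 0.834) = 8%, 1 − Φ(2.241 − 1.667) = 28% and 1 − Φ(2.241 − 2.501) = 60%.

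**Step 4. Locate the significance boundary.** With t(276) = 2.51 at two-sided 0.0125, the smallest significant observed difference is 0.200 × 2.51 = 0.50 NRS points, or 8.43 × 2.51 = 21.2 PASE points. The pain figure is a quarter of the 2 points that Sample Size calls clinically relevant.

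**The case against.** The strongest reply is that this is a wording slip in a short metadata field, probably meant for the blinded statistician. The same line states that subjects are not blind, and the Blinding section sets out what participants know and what is withheld. That stands: a reader might infer that the protocol conceals its open-label nature, and the documents do not support that. It also stands that a program-versus-nothing control cannot be participant-blinded, and that the Education arm, matched for duration and attention, is there to address non-specific effects.

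Two further readings go beyond the documents:

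- **That a half-point reporting shift would by itself produce a significant result.** Half a point is the smallest *observed* difference that reaches significance. A true shift of that size reaches it about half the time, and nothing in the documents says that a shift of that size is to be expected.
- **That significance against No-Intervention alone would count as success.** The success rule in Sample Size speaks of either or both *outcomes* and does not say that either comparator suffices. Hypothesis 2 names both comparators. Success on No-Intervention alone is therefore an inference.

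It would also be wrong to call Mindset versus Education unmasked, since its participants are kept from the content differences and the hypotheses. That the plan does not test whether this masking held is a design preference and not an error.

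None of this makes the assessor entry true. Disclosure elsewhere is a reason to correct the entry to match it.

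**Conclusion.** The concern holds as a false masking entry. No independent assessor exists to be blind. The participants who act as assessors are unmasked in every comparison with No-Intervention: two of the four corrected comparisons, and the primary mindset outcomes at T2. Mindset versus Education is partly masked. This conclusion rests on reading the protocol's sections together and on no numerical assumption.

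The practical size is unknown. The illustrative chances of about 5%, 20% and 50% depend on the assumed shifts of 0.1, 0.2 and 0.3 SD, on 139 per group, on the plan's SDs and on a two-sided test. They show that modest shifts could matter, not that they will occur. The sample size and the planned tests are unaffected. What changes is how the No-Intervention results may be described.

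**What to change.** 1. Replace the masking entry in Supplement 1 Table 1 with wording such as: *Outcomes are self-reported by participants, who know whether they received a program. The two program arms are masked to content differences and hypotheses. There is no independent outcome assessor. The data analyst is blinded to group labels.*
2. Add to Statistical Methods that the comparisons with No-Intervention rest on unmasked self-report and are open to expectation and reporting bias, and that any conclusion on pain or activity drawn from them must say so.

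Both are text changes and require no new data. The cost is that the stated masking becomes less favourable. Whether the registry carries the same entry cannot be checked from these documents; if it does, it should be brought into line.
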